## 5.2. Number of Participants

Up to 42 patients may be enrolled so that approximately 34 patients complete the study. For purposes of this study, a patient completes the study when all scheduled procedures shown in the Schedule of Activities (Section 2) are finished.

If patients discontinue the study before completion of both clamp periods, replacement patients may be enrolled up to 42 patients following agreement between the investigator and the sponsor. The replacement patients will be assigned the treatment sequence of the discontinued patient and complete that sequence in its entirety.

## 5.3. End of Study Definition

End of the study is the date of the last visit or last scheduled procedure shown in the Schedule of Activities (Section 2) for the last patient.

## 5.4. Scientific Rationale for Study Design

The use of a crossover design allows each patient to serve as his or her own control, thereby reducing variability. The study is patient- and investigator-blind to minimise potential bias. The Lilly clinical pharmacologist (CP)/Lilly study team will be unblinded.

A euglycaemic clamp technique, the gold standard methodology for assessing insulin action, will be used in this study to provide data on the GD activity of each study insulin lispro formulation. See Section 9.6 for a detailed description of the clamp methodology.

Patients with T2DM were selected based on the need to conduct PK, GD and safety assessments of LY900014 as part of our intended population.

Based on the PK properties of treprostinil (half-life associated with the terminal rate constant in non-compartmental analysis [ $t_{1/2}$ ] = approximately 1 hour) and Humalog ( $t_{1/2}$  = approximately 0.7 hours), a minimum of 3 days for the washout period between study dosing for each consecutive study periods and at least 14 days between the last dose of study drug and the follow-up visit are considered appropriate.

### 5.5. Justification for Dose

Based on previous studies of both insulin lispro (Humalog) and LY900014, the 15 U dose is within the clinical dose range and should provide measurable PK and GD profiles for both study insulins. The safety, PK and pharmacology of LY900014 at similar doses and with similar formulation composition have been assessed in 3 clinical studies in healthy subjects, and in patients with T1DM using MDI or insulin pump treatment and T2DM using MDI. In an MDI regimen, the total daily insulin dose is divided into approximately 50% delivered as the basal insulin dose and the other 50% divided among preprandial insulin doses. In this patient population, the weight-based total daily insulin dose for a large majority of patients is 0.6 to 1.2 U/kg/day, although some highly insulin-resistant patients may require more than 2.0 U/kg/day (Rosenstock et al. 2008). It is estimated that the body weight would be around 100 kg making the total daily prandial dose between 30 and 60 U/day or 10 to 20 U for 3 daily meals. Thus, the 15 U dose of LY900014 within this study would delivery approximately a 0.15 U/kg dose and would not exceed this high estimate for the total daily preprandial insulin.

CCI

## 6. Study Population

Eligibility of patients for study enrolment will be based on the results of screening medical history, physical examination, vital signs, clinical laboratory tests and electrocardiogram (ECG).

The nature of any conditions present at the time of the physical examination and any preexisting conditions will be documented.

Screening may occur up to 28 days prior to enrolment. Patients who are not enrolled within 28 days of screening may be subjected to an additional medical assessment and/or clinical measurements to confirm their eligibility.

Prospective approval of protocol deviations to recruitment and enrolment criteria, also known as protocol waivers or exemptions, is not permitted.

### 6.1. Inclusion Criteria

Patients are eligible for inclusion in the study only if they meet all of the following criteria at screening and/or enrolment:

[1] are male or female patients with T2DM for at least 1 year.

[1a] male patients:

No male contraception required except in compliance with specific local government requirements.

[1b] female patients:

- A. Women of childbearing potential who are abstinent (if this is complete abstinence, as their preferred and usual lifestyle) or in a same sex relationship (as part of their preferred and usual lifestyle) must agree to either remain abstinent or stay in a same sex relationship without sexual relationships with males.
- B. Otherwise, women of childbearing potential participating must agree to use 1 highly effective method (less than 1% failure rate) of contraception, or a combination of 2 effective methods of contraception for the entirety of the study.
  - a. Women of childbearing potential must test negative for pregnancy prior to initiation of treatment as indicated by a negative serum pregnancy test at the screening visit followed by a negative urine pregnancy test within 24 hours prior to exposure.
  - b. Either 1 highly effective method of contraception (such as combination oral contraceptives, implanted contraceptives or intrauterine device) or a combination of 2 effective methods of contraception (such as male or female condoms with spermicide, diaphragms with spermicide or cervical sponges) will be used. The patient may choose to use a double-barrier method of

contraception. Barrier protection methods without concomitant use of a spermicide are not a reliable or acceptable method. Thus, each barrier method must include use of a spermicide. It should be noted that the use of male and female condoms as a double-barrier method is not considered acceptable due to the high failure rate when these methods are combined.

- C. women not of childbearing potential may participate and include those who are:
- a. infertile due to surgical sterilisation (hysterectomy, bilateral oophorectomy or tubal ligation), congenital anomaly such as mullerian agenesis; or
  - b. post-menopausal – defined as either
    1. A woman aged less than 52 years; and being amenorrhoeic for more than 1 year with a serum follicle-stimulating hormone (FSH) level compatible with postmenopausal status; or
    2. Aged at least 52 years and being amenorrhoeic for at least 1 year with a FSH level compatible with post-menopausal status; or
    3. Aged at least 52 years and being amenorrhoeic for more than 1 year
- [2] are aged 18 to 70 years at the time of screening.
- [3] have a body mass index of 18.5 to 35.0 kg/m^2, inclusive, at screening.
- [4] have venous access sufficient to allow for glucose infusion and blood sampling procedures as per protocol.
- [5] are reliable and willing to make themselves available for the duration of the study and are willing to follow study procedures.
- [6] are able and willing to give signed informed consent approved by Lilly and the ethical review board (ERB) governing the site.
- [7] have clinical laboratory test results within normal reference range for the population or investigative site, or results with acceptable deviations that are judged to be not clinically significant by the investigator.
- [8] have a glycated haemoglobin (HbA1c) <9.0% at screening.
- [9] have had no episodes of severe hypoglycaemia in the past 6 months (see Section 9.4.5.3).

- [10] are on stable prandial insulin, plus/minus basal insulin (neutral protamine Hagedorn [NPH] insulin, insulin glargine or insulin detemir) with or without a stable dose of metformin, DDP-IV inhibitors, sulphonylureas and SGLT-2 inhibitors, for at least 3 months before screening. See Section 5.1 for OAD washout details.
- [11] have a fasting C-peptide  $\leq 1.0$  nmol/L. Patients who had C-peptide levels  $>1.0$  nmol/L may be re-tested once. If the re-test yields a C-peptide  $\leq 1.0$  nmol/L, then the patient satisfies this criterion.

## 6.2. Exclusion Criteria

Patients will be excluded from study enrolment if they meet any of the following criteria at screening and/or enrolment:

- [12] are investigative site personnel directly affiliated with this study and their immediate families. Immediate family is defined as a spouse, biological or legal guardian, child or sibling.
- [13] are Lilly employees or employees of the investigational site/CRU.
- [14] are currently enrolled in a clinical trial involving an investigational product (IP) or any other type of medical research judged not to be scientifically or medically compatible with this study.
- [15] have participated within the past 30 days in a clinical trial involving an IP. If the previous IP has a long half-life, 3 months or 5 half-lives (whichever is longer) should have passed.
- [16] have previously completed or withdrawn from this study.
- [17] have an abnormality in the 12-lead ECG that, in the opinion of the investigator, increases the risks associated with participating in the study.
- [18] have a supine blood pressure at screening outside the range of 90 to 160 mmHg for systolic or 50 to 95 mmHg for diastolic (1 repeat is allowed) as determined by the investigator, or results with unacceptable deviations that are judged by the investigator to be clinically significant for the population, or have a heart rate outside the range of 50 to 90 beats/minute.
- [19] have donated blood of more than 450 mL or more in the past 3 months or provided any blood donation within the past 1 month before screening.
- [20] have a history or current cardiovascular, respiratory, hepatic, renal, gastrointestinal, endocrine (apart from T2DM), haematological or neurological disorders capable of significantly altering the absorption, metabolism or elimination of drugs; of constituting a risk when taking the IP; or of interfering with the interpretation of data.
- [21] have known or ongoing psychiatric disorders.

- [22] regularly use known drugs of abuse and/or show positive findings on urinary drug screening.
- [23] are currently a smoker, used tobacco products on a regular basis in the 6 months before screening, or are intending to smoke during the study period.
- [24] have a significant history of alcoholism or drug abuse as judged by the investigator or consuming more than 24 g of alcohol per day for men, or more than 12 g of alcohol per day for women (1 unit of alcohol is defined as 10 mL [8 g] of pure alcohol).
- [25] are unwilling to comply with the dietary requirements/restrictions during the study: (i) comply with the fasting requirements of the study, (ii) consume only the meals/snacks provided during the inpatient visits.
- [26] show evidence of an acute infection with fever or infectious disease at the time of study entry.
- [27] show evidence of human immunodeficiency virus (HIV) infection and/or positive human HIV antibodies.
- [28] show evidence of hepatitis C and/or positive hepatitis C antibody (the presence of hepatitis C antibodies in the setting of normal liver function tests and a negative hepatitis C polymerase chain reaction are not an exclusion).
- [29] show evidence of hepatitis B and/or positive hepatitis B surface antigen (the presence of antibodies to the hepatitis B surface antigen is not an exclusion).
- [30] are women who are pregnant or lactating.
- [31] have significant lipohypertrophy in the target abdominal injection area as judged by the investigator.
- [32] have a history of renal impairment (exclusion only if estimated glomerular filtration rate [estimated GFR]  $<60$  mL/minute/1.73 m^2 [GFR is estimated according to the Chronic Kidney Disease Epidemiology Collaboration creatinine equation]), or have a serum creatinine level  $\geq 0.000126$  mol/L (male) or  $\geq 0.000111$  mol/L (female).
- [33] have a history of deep vein thrombosis of the leg or repeated episodes of deep leg vein thrombosis in first-degree relatives (parents, siblings or children) as judged by the investigator.
- [34] have proliferative retinopathy or maculopathy and/or severe neuropathy; in particular, autonomic neuropathy as judged by the investigator based on a recent ( $<1.5$  years) ophthalmologic examination.
- [35] are receiving chronic (lasting longer than 14 consecutive days) systemic or inhaled glucocorticoid therapy (excluding topical, intra-articular and intraocular preparations), or have received such therapy within the 4 weeks before screening.

- [36] have, except for current regimen of insulin therapy and concomitant medication(s) (for example, antihypertensive medication, lipid-lowering agent, thyroid hormone replacement medication, hormonal contraception, hormonal replacement therapy), regular use of or intended use of any over-the-counter or prescription medications or nutritional supplements that treat hyperglycaemia or insulin resistance or that promote weight loss within 14 days before dosing (apart from vitamin/mineral supplements, occasional acetaminophen [paracetamol] or ibuprofen).
- [37] have known allergies to treprostinil (CCI [REDACTED]), insulin lispro, insulin glulisine, related compounds or any components of the formulation, or a history of significant atopy.
- [38] any significant changes in insulin regimen and/or unstable blood glucose control within the past 3 months prior to screening as assessed by the investigator.
- [39] require daily insulin treatment  $\geq 1.2$  U/kg/body weight.
- [40] are treated with a CSII (insulin pump).
- [41] currently receiving insulin degludec therapy or insulin degludec combinations, or have been treated with degludec within the past 30 days.
- [42] currently receiving dulaglutide therapy or have been treated with dulaglutide within the past 30 days.
- [43] in the opinion of the investigator or sponsor, are unsuitable for inclusion in the study.

### 6.3. Lifestyle and/or Dietary Requirements

Throughout the study, patients may undergo medical assessments and review of compliance with requirements before continuing in the study.

#### 6.3.1. Meals and Dietary Restrictions

Patients will fast for approximately 8 hours prior to dosing until after the glucose clamp procedure is completed, after which patients will receive a meal. Water can be consumed freely during this time. If the clamp procedure is completed in less than 10 hours, then the meal should be delayed until the last PK sample has been taken, unless the investigator deems it necessary to administer the meal for safety reasons. Patients will take their regular prandial insulin with the end-of-study meal and site will record the dose and time in the patients eCRF.

When not a resident at the CRU, patients will be encouraged to follow their normal diets.

#### 6.3.2. Caffeine, Alcohol and Tobacco

No alcohol will be allowed at least 24 hours before each dose and throughout the duration of each CRU visit. Between dosing visits, daily alcohol should not exceed 3 U for males and 1.5 U for females (a unit is defined in Exclusion Criterion [24]).

Patients should refrain from caffeine-containing food/beverages (for example, cola, chocolate, tea and coffee) for at least 12 hours before each dose and throughout the duration of each CRU visit.

Smoking (cigars, cigarettes or pipes) and the use of smokeless tobacco will not be permitted during the study.

### **6.3.3. Activity**

Patients are encouraged to maintain their regular exercise habits; however, they should not undertake vigorous or prolonged exercise within 48 hours prior to each dosing day. After dosing, patients should remain recumbent or sitting in the CRU until the end of the glucose clamp.

Movement will be restricted to retain the integrity of connections to the infusion(s) and the study procedures.

### **6.3.4. Washout Period**

During the insulin-transition and wash-out period hyperglycaemia will be monitored daily by fasting fingerstick blood glucose measured and documented in a diary. Each patient will be instructed to contact the investigational site staff if his/her fasting fingerstick glucose level is >240 mg/dL. The patient will be managed as considered appropriate by the Investigator based on the actual glucose value (e.g., return to the study center for evaluation). If the patient has a fasting fingerstick glucose level >240 mg/dL on two consecutive days, the patient will be instructed to return to the study center the following day to have a fasting plasma glucose performed. If the fasting plasma glucose >240 mg/dL is confirmed, the patient will be withdrawn from the study.

## **6.4. Screen Failures**

Individuals who do not meet the criteria for participation in this study may be rescreened 1 time. Individuals who still do not meet participation criteria after rescreening (screen failure) may not be rescreened.

## 7. Treatment

### 7.1. Treatment Administered

This study involves a comparison of 15 U LY900014 and 15 U Humalog each administered once through SC injection. Table ITRU.2 shows the treatment regimens.

**Table ITRU.2. Treatments Administered**

Regimen	Dose Strength	Dose Administration	Route of Administration
LY900014	100 U/mL	15 U	Subcutaneous
Humalog	100 U/mL	15 U	Subcutaneous

The investigator or designee is responsible for

- explaining the correct use of the IP(s) to the site personnel
- verifying that instructions are followed properly
- maintaining accurate records of IP dispensation and collection, and
- returning all unused medications to Lilly or its designee at the end of the study

**Note:** Sites may destroy the material if, during the investigative site selection, the evaluator has verified and documented that the site has appropriate facilities and written procedures to dispose of clinical trial materials.

#### 7.1.1. Packaging and Labelling

Clinical trial materials will be labelled according to the country's regulatory requirements. LY900014 will be supplied by Lilly or its representative in accordance with current good manufacturing practices and will be supplied with lot numbers. Humalog (commercially available) will be supplied by Lilly.

The study insulin will be provided to the site unblinded. CCI

An unblinded pharmacist at the site or other site personnel who are unblinded will use the insulin vials provided to prepare the blinded syringes.

### 7.2. Method of Treatment Assignment

The treatment to be injected on a given treatment day will be determined according to a randomisation schedule.

### **7.2.1. Selection and Timing of Doses**

The actual date and time of all dose preparation will be documented, and the actual time of all dose administrations will be recorded in the patient's electronic case report form (eCRF). For each patient, the aim is to administer study doses at approximately the same time on Day 1 of each study period.

All study treatments will be given in the CRU by qualified unblinded site personnel as designated by the investigator. Study injections should be given by a limited number of individuals for consistency.

The site of administration of each injection will be recorded. The insulin used in this study will be injected using syringes and vials. Injection sites selected should be about 5 cm from the umbilicus. The same size syringe/needle combination will be used for all patients across periods and will ensure consistent injection depth into the SC space. Injections will be rotated among different injection sites on the anterior abdominal wall during the 2 study periods (that is, left lower quadrant and right lower quadrant).

### **7.3. Blinding**

This is a patient- and investigator-blind study. The Lilly CP/Lilly study team will be unblinded.

Emergency codes will be available to the investigator. A pharmacist or other site personnel who is unblinded will be required to prepare the insulin doses for administration. A code that reveals the treatment group for a specific study patient may be opened during the study only if the patient's well-being requires knowledge of the patient's treatment assignment. The site personnel who performs the drug administration will not be blinded and will be separate and distinct from those who are involved in patient care and patient assessments.

In case of an emergency, the investigator has the sole responsibility for determining if unblinding of a patient's treatment assignment is warranted for medical management of the event. The patient's safety must always be the first consideration in making such a determination. If the investigator decides that unblinding is warranted, it is the responsibility of the investigator to promptly document the decision and rationale and notify Lilly as soon as possible.

Upon completion of the study, all codes must be returned to Lilly or its designee.

### **7.4. Dose Modification**

Dose adjustments are not allowed in this study.

### **7.5. Preparation/Handling/Storage/Accountability**

Only participants enrolled in the study may receive IP, and only authorised site staff may supply or administer study treatment. All study treatments should be stored in an environmentally controlled and monitored (manual or automated) area in accordance with the labelled storage conditions with access limited to the investigator and authorised site staff.

All insulin products must be stored at the investigative site under refrigerated conditions (between 2°C and 8°C) in a locked and secure place. Insulin must not be frozen.

The investigator will be responsible for study treatment accountability, reconciliation and record maintenance (such as receipt, reconciliation and final disposition records).

## 7.6. Treatment Compliance

The study drugs will be administered at the clinical site, and documentation of treatment administration will occur at the site.

## 7.7. Concomitant Therapy

Patients on stable concomitant medication(s) at the time of study entry should continue their regular, unchanged dose throughout the study (including metformin). Patients receiving multiple daily insulin injections will discontinue their basal and prandial insulin regimens as described in the study design, prior to receiving study treatment (Section 5.1). Additionally, patients receiving OAD will discontinue use (with the exception of metformin) according to guidance in Section 5.1. Similarly, where applicable the patient's insulin regimen should resume in between dosing periods and discontinued prior to the next period following the guidance in Section 5.1.

Patients should not use over-the-counter or prescription medications (other than their current regimen of insulin therapy) and concomitant medication(s). For example, anti-hypertensive medication, lipid-lowering agent, thyroid hormone replacement medication, hormonal contraceptives or nutritional supplements that affect blood glucose or the body's sensitivity to insulin or that promote weight loss 14 days before dosing (apart from vitamin/mineral supplements, occasional acetaminophen [paracetamol], ibuprofen or hormonal replacement therapy) or throughout the study (refer to Section 6.2).

Patients should not be receiving chronic (lasting longer than 14 consecutive days), systemic or inhaled glucocorticoid therapy (excluding topical, intra-articular and intraocular preparations) or have received such therapy within the 4 weeks before screening.

Patients should not apply any creams or lotions to the abdominal skin on the morning of the study treatment dosing or during the inpatient study procedure.

If the need for concomitant medication arises, inclusion or continuation of the patient may be at the discretion of the investigator, and when possible, after consultation with a Lilly CP. Any additional medication used during the course of the study must be documented.

Any changes in concomitant medications from screening will be recorded upon admission to the CRU.

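### Protocol 7.7, second paragraph, is garbled and on its plain reading conflicts with its own first sentence, criterion [36] and the contraception rule over four medication classes

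*Protocol*

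**What the plan says.** Protocol 7.7 opens with a continuation rule: "Patients on stable concomitant medication(s) at the time of study entry should continue their regular, unchanged dose throughout the study (including metformin").

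Its second paragraph then gives a prohibition, followed by the start of a list of examples: "Patients should not use over-the-counter or prescription medications (other than their current regimen of insulin therapy) and concomitant medication(s). For example, anti-hypertensive". The bracket that holds the exception closes after insulin therapy, so concomitant medication falls outside the exception. The list of examples is a sentence fragment: "For example, anti-hypertensive medication, lipid-lowering agent, thyroid hormone replacement medication, hormonal contraceptives or nutritional supplements that affect blood glucose", and it goes on to effects on insulin sensitivity and weight. The window is 14 days before dosing or the whole study. The closing exemption reads "apart from vitamin/mineral supplements, occasional acetaminophen [paracetamol], ibuprofen or hormonal replacement therapy) or throughout the study (refer to Section 6.2").

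Criterion [36] in Protocol 6.2 excludes use, within 14 days before dosing, of products that treat hyperglycaemia or insulin resistance or that promote weight loss. It first makes an exception for current insulin and for concomitant medication, with the examples "antihypertensive medication, lipid-lowering agent, thyroid hormone replacement medication, hormonal contraception, hormonal replacement therapy".

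Inclusion criterion [1b] B in Protocol 6.1 asks women of childbearing potential, outside the abstinent or same-sex group, to use contraception for the whole study. It accepts one highly effective method, "such as combination oral contraceptives, implanted contraceptives or intrauterine device", or a combination of two effective methods.

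**The concern.** The same four classes stand in an exception in 6.2 and in what reads as a prohibition in 7.7. Section 7.7 is the section that governs concomitant therapy during the study, so it is an operative instruction and not background. For a patient who enters on stable treatment in one of these classes, its first paragraph says to continue, and its second, read plainly, says not to use it. The site cannot follow both.

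Two things are at stake. One is patient care: maintenance medication, or the contraception on which a woman qualified, could be stopped because of a badly built sentence. The other is the trial record: continued use could be logged as a deviation from the second paragraph, and stopping it would depart from the first.

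**Working it through.** No arithmetic applies, so the check sets the texts side by side.

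| Class | 7.7, second paragraph (plain reading) | 7.7, first sentence | Criterion [36] | [1b] B.b |
|---|---|---|---|---|
| Antihypertensives | not to be used | continue if stable | excepted | not addressed |
| Lipid-lowering agents | not to be used | continue if stable | excepted | not addressed |
| Thyroid replacement | not to be used | continue if stable | excepted | not addressed |
| Hormonal contraceptives | not to be used | continue if stable | excepted | accepted as one option |

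Hormone replacement therapy is not in conflict: 7.7 exempts it and [36] excepts it.

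Step 1, exemptions. The second paragraph of 7.7 exempts current insulin, vitamins and minerals, occasional paracetamol, ibuprofen and hormone replacement. None of the four classes is among them.

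Step 2, time windows. A difference in scope could explain the mismatch if [36] governed entry only and 7.7 governed conduct only. It does not. Both texts cover the 14 days before dosing, so they meet head-on in that window. For the rest of the study, the second paragraph of 7.7 meets its own first sentence and, for contraceptives, the requirement in [1b] B to use contraception throughout.

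Step 3, the qualifying phrase. The words about glucose, insulin sensitivity and weight can attach in two ways.

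- To nutritional supplements only: the four classes are then barred without limit, and the conflict is complete.
- To the whole list: only members of the four classes with such an effect are then barred. The conflict is smaller but remains. The sentence before the fragment carries no such limit, and [36] excepts the classes whatever their effect on glucose. The site would also have to judge each drug, and the protocol gives no guidance for that.

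Step 4, the discretion clause. Section 7.7 lets the investigator decide on inclusion or continuation when a need for concomitant medication arises. That addresses a new need, not maintenance treatment already in use at entry.

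**The case against.** The strongest reply is that this is a punctuation slip and that nobody would act on it. The fragment has no main verb. Moving one bracket and deleting one full stop would give it much the same structure as [36]. A reader of 7.7 meets the continuation rule first and a pointer to Section 6.2 last. Section 7.7 also has changes in concomitant medication recorded at admission, which presupposes that such medication is in use.

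Much of this stands. The text looks like a drafting error and not a considered ban, and a careful site may resolve it by following the cross-reference. But that resolution depends on the reader setting aside the words of one paragraph in favour of another, and the protocol does not say which prevails.

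Three stronger readings are tempting, and the documents do not support them.

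- A reader might infer that the protocol requires hormonal contraception and then forbids it. It does not require it: an intrauterine device, or two effective methods, also qualifies.
- A reader might infer that a large share of patients is affected. The documents give no counts for any of the four classes.
- A reader might infer that the pharmacokinetic or glucodynamic sets would lose patients, because SAP Section 8 takes deviations into account when assigning populations. That section weighs deviations by severity and impact and states no exclusion rule for medication. Nothing shows that a set would change.

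**Conclusion.** The second paragraph of 7.7 conflicts, on its plain reading, with three other places in the protocol. The conflict covers four named classes. It is complete if the qualifying phrase applies to supplements only, and partial if it applies to the whole list. The conclusion rests on the bracket and full stop standing where the text shows them, and on reading the fragment as illustrating the sentence before it.

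The consequence is a possible one: medication stopped, or deviations logged, at a site that takes the paragraph literally. The number of patients is unknown, no effect on the primary comparison is shown, and no figure in the plan depends on the point. It still merits correction, because the instruction concerns maintenance medication and contraception and cannot be followed together with the paragraph before it.

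**What to change.** Reconcile the second paragraph of 7.7 with the first sentence of 7.7, with criterion [36] and with [1b] B.b. The sponsor should state the status of each of the four classes, and say whether the limit on glucose, insulin sensitivity and weight applies to the whole list or to supplements only. Sections 6.2 and 7.7 should then carry the same wording, consistent with 6.1. Which rule applies is a clinical decision for the sponsor, and this review proposes none.

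The cost is one rewritten sentence, in a protocol amendment or a clarification letter to sites. It adds no procedures and changes nothing in the SAP.
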